### 10.7.2 Assessment and management of risk

#### Risk associated with the imaging techniques

Subjects in this study will be exposed to an additional dose of ionising radiation as a result of their participation. The majority of the radiation dose comes from the administered radioligand, while a smaller portion comes from a low dose computed tomography (CT) scan performed to estimate tissue attenuation. To mitigate this risk, the study will exclude subjects who have had previous exposure to ionising radiation such that, their exposure would be  $> 10\text{mSv}$  for the previous year. A maximum of 100 MBq of [ $^{18}\text{F}$ ]-IMA601 will be injected for each PET scan and the maximal effective dose from ionising radiation for an individual will not exceed 7.4 mSv from the PET and low-dose CT scans. The maximal radiation exposure for each subject over the whole study is presented in Table 2.

**Table 2: Expected maximal radioactive exposure of each subject**

Assessment	Number of scans	Effective dose per injected activity (mSv/MBq)	PET tracer Activity (MBq)	Effective dose per scan (mSv)	Total exposure (mSv)
PET emission scan	3	0.021	100	2.1	6.3
Low-dose CT scan	3			0.36	1.08
TOTAL					7.4

A maximal study exposure of 7.4 mSv for a participant, places this study towards the top of Category IIb ( $< 10\text{ mSv}$ ) of the guidance published by the International Commission for Radiation Protection (ICRP). Following the ICRP 62 guidance that provides a guideline of  $\leq 10\text{ mSv}$  per study where research subjects are not expected to benefit personally.

Magnetic resonance images delineating brain anatomy will be acquired in this study to aid PET image analysis. There are no known risks to subjects associated with MRI scanning, provided that they have no contraindications to MRI as listed in the exclusion criteria. Potential risks associated with metallic implants will be mitigated by administration of a questionnaire and careful screening. At all times while subjects are on the ward, registered nurses will provide care and supervision.

#### Risk associated with arterial cannulation

Before the PET-CT scan, subjects will have a cannula inserted into the radial artery by qualified staff using aseptic technique under local anaesthesia. That insertion may be uncomfortable, cause minor local bleeding and bruising, and can rarely lead to complications (e.g., a blood clot could form around the cannula). Most people have no after-effects of cannulation. However, very occasionally, it may cause a small scar. Very rarely, more serious complications can occur, although these usually occur when the radial artery is cannulated in sick people for therapeutic purposes, rather than in healthy subjects for research purposes.

## 11.0 ADVERSE EVENT DEFINITIONS, REPORTING, AND FOLLOW-UP

All AEs, SAEs, SARs, and pregnancies occurring during the protocol-specified timeframes ([Table 1](#)) will be assessed and reported per guidelines provided in the following sections.

### 11.1 Definitions

#### 11.1.1 Adverse Event Associated with Study Procedures

A procedure-related AE is an AE considered by the Investigator to be related to a procedure required by the protocol (i.e., temporally associated or known risk of the procedure).

#### 11.1.2 Adverse Event

An AE is any untoward medical occurrence associated with the use of a drug in humans, whether or not considered drug related. The term “adverse event” could include any of the following events that develop or increase in severity during the course of the trial. Examples include:

- Any sign, symptom, or physical examination finding that worsens in nature, severity, or frequency compared to baseline irrespective of association with the condition under study
- Any clinically significant laboratory abnormality or laboratory abnormality that requires medication or hospitalization
- Reactions to study drug(s) including those occurring as a result of an overdose, abuse, withdrawal phenomena, sensitivity, or toxicity
- Concurrent illness
- Injury or accident

Conditions present prior to enrollment are considered Medical History. Pre-existing conditions should be reported as a TEAE if there is a change in the frequency, intensity, or the character of the condition.

#### 11.1.3 Serious Adverse Event

A SAE is an AE that:

- results in death
- is considered life threatening
- requires in-patient hospitalization or prolongation of existing hospitalization
- results in persistent/significant disability/incapacity
- results in a congenital anomaly/birth defect; or
- other medically important serious medical event

### 11.2 Assessment of Adverse Events

For each AE, the Investigator will assess the severity, causality, and outcome.

### 11.2.1 Severity

AEs should be graded as mild, moderate, severe, life-threatening, or death using the following definitions:

- Mild: asymptomatic or mild symptoms; clinical or diagnostic observations only; intervention generally not indicated
- Moderate: minimal, local, or noninvasive intervention indicated; limiting age-appropriate instrumental activities of daily living
- Severe: interrupts normal daily activities and generally requires systemic drug therapy or other treatment; usually incapacitating.
- Life-threatening: urgent intervention indicated
- Death: events that results in death

Severity is not considered a guide for defining regulatory reporting obligations.

### 11.2.2 Causality

The Investigator should consult the IB when assessing relationship to study drug and consider all possible etiologies for the AE. The Investigator will assess the causality of the AE to study procedure or study drug as follows:

1) Attributions for “Unrelated” events:

- **Unrelated:** the AE *is clearly not related* to the study drug/procedure, beyond a reasonable doubt
- **Unlikely Related:** the AE *is doubtfully related* to the study drug/procedure

2) Attributions for “Related” events:

- **Possibly Related:** the AE *may be related* to the study drug/procedure
- **Probably Related:** the AE *is likely related* to the study drug/procedure
- **Definitely Related:** the AE *is clearly related* to the study drug/procedure

For the purposes of reporting to regulatory agencies, AEs deemed as Definitely, Probably or Possibly Related will be considered Related and those deemed Unrelated or Unlikely Related will be considered Unrelated.

AEs listed as related are considered to have a suspected “reasonable causal relationship” to the study drug/intervention (ICH E2A). The expression “reasonable causal relationship” is meant to convey in general that there are facts (evidence) or arguments to suggest a causal relationship.

### 11.2.3 Outcome

The outcome of an AE associated will be assessed as follows:

- Recovered/Resolved: the event has improved or recuperated
- Not recovered/Not Resolved: the event has not improved or recuperated
- Recovered/resolved with sequelae: the participant recuperated but retained pathological conditions resulting from the prior disease or injury
- Fatal: termination of life as a result of an AE
- Unknown: not known, not observed, not recorded

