### **7.6.1 Removal of Subjects**

The Investigator and Sponsor also have the right to remove subjects from the trial. The Sponsor also reserves the right to discontinue participation of an individual subject.

Subjects may be removed from the trial for the following reasons:

- Occurrence of an AE or SAE that precludes further participation
- Serious adverse event (SAE) considered related to study treatment.

- Any condition that, in the judgment of the Investigator or Sponsor, might place the subject at risk or invalidate the trial
- Pregnancy in subject
- At the request of the subject, Investigator, or Sponsor, for administrative or other reasons
- Protocol deviation or noncompliance
- One or more study drug administrations are missed
- Alanine aminotransferase (ALT)  $\geq 5 \times$  upper limit of normal (ULN).
  - ALT  $\geq 3 \times$  ULN and total bilirubin  $\geq 2 \times$  ULN or international normalised ratio (INR)  $> 1.5$ . (If a subject meets that withdrawal criterion, serum bilirubin fractionation should be performed.)
  - ALT  $\geq 3 \times$  ULN if associated with the appearance or worsening of rash or hepatitis symptoms (fatigue, nausea, vomiting, right upper quadrant pain or tenderness, fever, rash or eosinophilia). Subjects who have -ALT  $\geq 3 \times$  ULN and  $< 5 \times$  ULN, total bilirubin  $< 2 \times$  ULN or INR  $< 1.5$ , who do not exhibit hepatitis symptoms or rash, can continue in the study (and continue receiving trial medication) as long as they can be monitored at least weekly until abnormal results are within the reference range or close to pre-treatment values.

Subjects that experience an AE or SAE as defined above will be followed-up by the Investigator until the AE/SAE has resolved. If a subject discontinues from the trial prematurely, reasonable efforts should be made to perform the Early Termination Visit procedures, within four weeks of discontinuation.

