#### **10.3.10 Adverse Events**

All events meeting the definition for AE, SAE, and pregnancy will be assessed and reported following guidelines provided in [Section 11.0](#). At Day -1, during the confinement period at regular intervals, and at follow-up, subjects will be asked about any new or ongoing AEs since the previous inquiry. Four weeks after last dose of tracer administration, an inquiry via phone will be done for the identification of potential SAEs.

Clinically significant changes from baseline in any safety or clinical laboratory parameter will be recorded as AEs or SAEs, if deemed appropriate by the Investigator.

Subjects who discontinue due to a treatment-emergent SAE will be followed-up by the Investigator until the SAE has resolved ([Section 7.6.1](#)).

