### 11.3 Adverse Event Reporting and Follow Up

All AEs (i.e., any new or worsening in severity or frequency of a preexisting condition) with onset after the subject signs consent for trial participation must be promptly documented on the AE electronic case report form (eCRF). Details of the AE must include severity, relationship to study drug, duration, and outcome. Serious Adverse Events Reporting

SAEs must be reported to the Sponsor (or designee) within 24 hours of the knowledge of the occurrence.

An SAE report will be completed as thoroughly as possible including all available details about the event and the signature of the Investigator. The SAE form will be updated when additional information is received.

A death occurring during the trial must be reported to Sponsor or its designee within 24 hours of knowledge of the death whether or not it is considered treatment-related.

The Investigator also must notify the IRB/IEC of the occurrence of the SAE, in writing, as soon as is practicable and in accordance with IRB/IEC requirements and local law. A copy of this notification must be provided to Sponsor or its designee.

Subjects will be instructed to contact the Investigator site and report any adverse events that develop after being discharged from the clinical unit. The Investigator will advise the subject on appropriate treatment, if necessary, and will follow the subject up until the adverse event resolves or the subject is lost to follow-up. If, in the investigator's opinion, the adverse event could be related to sterility issues with  $[^{18}\text{F}]\text{-IMA601}$ , the investigator will inform [REDACTED] In the event of a positive sterility result, [REDACTED] Quality Assurance department will be informed and an investigation following the process as outlined in [REDACTED] standard operating procedures will be initiated.

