Treatment	Subject	Scan number	{Add. time var.}	Start Date/ Start Time of PET scan	Stop Date/ Stop Time of PET scan	Dose drawn up	Residual 1	Residual 2	Brain Region	V _T (units)	Change from baseline V _T (units)
				[REDACTED]	[REDACTED]						

Template L_PD2

Listing 16.2.xx Listing of receptor occupancy and plasma concentration data of ASN51

Treatment	Subject	Scan number	{Add. time var.}	Start Date/ Start Time of PET scan	Stop Date/ Stop Time of PET scan	Concentration at start of PET scan	Occupancy (%)
				[REDACTED]	[REDACTED]		

Programming notes: Concentration at start of PET scan will be calculated using the closest time before start of PET scan and the closest time after PET scan

Template L_AE1_PG

Listing 16.2.x.xx Listing of all adverse events

Treatment	Subject	System Organ Class* / Preferred Term/ Verbatim Text	Outcome/ Onset Date/Time/ Resolved Date/Time/ Duration	Study Day Started/ Time Since Last Dose	Severity/ Serious/ Withdrawal	Frequency/ Action Taken (1)/ Other Action Taken	Related to Study Drug/ Treatment Emergent?
		Gastrointestinal Disorders / Intestinal Spasm / Enterospasm	Resolved/ [REDACTED]	Day x/ 10d 7h 3m	Mild/ No/ Yes	Intermittent/ Dose not changed/ None	Possibly/ Yes
Treatment 1	[REDACTED]						

(1) Action Taken with Study Treatment

*Coded using MedDRA vXX.X

Programming notes: For the listing of "other significant AEs" include (from ICH E3) AEs leading to withdrawal, AEs leading to dose reduction (including drug withdrawn, interrupted, reduced or similar) and AEs with AEOSE=Y. If AEOSE has not been collected then use "Otherwise significant" in the CRF.

Template L_LB1_PG

Listing 16.2.x.xx Listing of clinical chemistry data outside the normal range

Treatment	Subject	Laboratory test (units)	Planned Relative Time	Date/Time	Study Day	Value	Reference Interval	RI	Clinically Significant?
Treatment 1	[REDACTED]	Alk Phos (U/L)	Time 1	[REDACTED]	-1	64.00	32.0 - 92.0		
			Time 2	[REDACTED]	85	84.00	32.0 - 92.0		
	[REDACTED]	ALT (U/L)	Time 1	[REDACTED]	-1	29.00	10.0 - 40.0		
			Time 2	[REDACTED]	85	70.00	10.0- 40.0	H	Y
				[REDACTED]					

RI for Reference Interval flag;
 H = Above reference interval, L = Below reference interval

Programming notes: Lists only subjects with at least a high or low value

Template L_VS1_PG

Listing 16.2.x.xx Listing of vital signs outside the normal range

Treatment	Subject	Planned Relative Time	Date/Time	Systolic Blood Pressure (mmHg)	Diastolic Blood Pressure (mmHg)	Etc (units)

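### The adverse-event outcome scale has no category for an event that is improving but still present, and read literally it codes such an event as Recovered/Resolved

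*Protocol*

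**What the plan says.** Protocol section 11.2.3 gives five outcomes for an adverse event. Three matter here:

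- For an event that is better or over: "Recovered/Resolved: the event has improved or recuperated"
- For an event that is neither better nor over: "Not recovered/Not Resolved: the event has not improved or recuperated"
- For recovery that leaves a lasting condition: "Recovered/resolved with sequelae: the participant recuperated but retained pathological conditions resulting from the prior disease or injury"

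The other two are Fatal and Unknown.

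Three other sections use resolution to mark how long an event is followed:

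- Section 7.6.1, on removed subjects: they "will be followed-up by the Investigator until the AE/SAE has resolved".
- Section 10.3.10, on subjects who discontinue because of a treatment-emergent SAE: they "will be followed-up by the Investigator until the SAE has resolved".
- Section 11.3, on events after discharge: the investigator "will follow the subject up until the adverse event resolves or the subject is lost to follow-up".

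Section 11.3 also fixes what is recorded: "Details of the AE must include severity, relationship to study drug, duration, and outcome". In the SAP, listing template L_AE1_PG (section 17.2.3) prints these items in one column: "Outcome/ Onset Date/Time/ Resolved Date/Time/ Duration".

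**The concern.** An event can be better without being over. The outcome scale treats the two as the same, because the definition of Recovered/Resolved joins improvement and recuperation with an *or*. A site that follows the text would record an improving event as resolved.

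Three things are at stake:

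- **Outcome.** Events still present at discharge or at the follow-up visit may be reported as resolved.
- **Resolved date and duration.** If the date of improvement is entered as the resolved date, the listed duration is too short.
- **Meaning of resolved.** Section 11.2.3 is the only place where the protocol says what resolved means. If its definition is carried into sections 7.6.1, 10.3.10 and 11.3, those rules no longer clearly say what they appear to say.

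Safety and tolerability is a secondary objective. With at most 10 subjects, the individual listings carry much of the safety evidence, so single entries count for more than they would in a large trial.

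**Working it through.** There is no figure to reproduce. The check maps each state an event can be in to the categories of section 11.2.3, and then reads the result against the follow-up rules and the SAP.

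**Step 1. Map the states.**

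| State of the event | Category that fits as written |
|---|---|
| Unchanged or worse | Not recovered/Not Resolved |
| Improved, still present | Recovered/Resolved only |
| Fully gone | Recovered/Resolved |
| Recuperated, lasting condition remains | Recovered/resolved with sequelae |
| Death from the event | Fatal |
| No information | Unknown |

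The second row is the problem. Not recovered/Not Resolved fails because the event has improved. The sequelae category fails because the subject has not recuperated. Fatal and Unknown do not apply. Rows two and three end in the same code, so the data cannot tell an improving event from one that is over.

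**Step 2. Set this beside the follow-up sections.** Sections 7.6.1, 10.3.10 and 11.3 all run until resolution, and none gives its own definition. In ordinary use, an event that is still present has not resolved. Under section 11.2.3 it has. The two uses of the word disagree.

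**Step 3. Trace the listing.** Suppose that an event starts at time *a*, improves at *b* and is gone at *c*, and that *b* is entered as the resolved time. Then:

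- listed duration = *b* − *a*
- true duration = *c* − *a*
- shortfall = (*c* − *a*) − (*b* − *a*) = *c* − *b*

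The documents give no values for *a*, *b* or *c*, and no expected number of such events. The shortfall therefore cannot be sized.

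**Step 4. Trace the summary tables.** SAP section 13.2 summarises treatment-emergent events by number of events and number of subjects, by system organ class and preferred term. Shell T_AE1 has the same content. No planned table uses outcome or duration. An event coded as resolved too early still counts as one event in one subject, so incidence does not fall.

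**Step 5. Check the direction.** Outcome and duration err towards a milder picture. The event count can err the other way. If an event coded as resolved worsens again, for example after the session 3 dose 7–14 days after session 2, it may be entered as a new event and raise the bracketed count in T_AE1.

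**The case against.** The best defence is that section 11.2.3 is a reporting scale and not a stopping rule. The follow-up sections do not cite it, and the label Not recovered/Not Resolved plainly describes an event that is still there. Section 10.3.10 also has staff ask about continuing as well as new events on Day -1, through confinement and at follow-up. A sensible site would therefore keep an improving event open.

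Part of this stands. A reader might infer that improving events will receive an end date and drop out of follow-up. The documents do not support that as a certainty: no section ties the outcome code to an end date or to the close of follow-up, and the eCRF completion rules are not among the documents. Both consequences are possible, and neither is stated.

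The defence does not rescue the definition. It relies on sites setting the definition aside in favour of the label, and different staff may choose differently.

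A second objection concerns ALT. Section 7.6.1 has subjects in its 3 to 5 × ULN band who continue in the study monitored at least weekly until values are normal again or near their pre-treatment level. A reader might infer that this monitoring would lapse once ALT had improved. It would not, because it has its own end point, independent of the outcome code. Out-of-range chemistry values are also listed and summarised separately under SAP section 13.5. What remains is a coding mismatch: an ALT value that has fallen but is still raised counts as improved under section 11.2.3 while section 7.6.1 still has it under monitoring.

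**Conclusion.** The definition is wrong as written. An improving but persistent event literally fits only Recovered/Resolved, and no other section corrects this. It may lead to a wrong resolved date and a shortened duration in listing L_AE1_PG, and it conflicts with the wording of sections 7.6.1, 10.3.10 and 11.3.

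The statistical effect is small. The adverse-event summary tables are largely unaffected, since they count events and subjects, and the occupancy analysis is untouched. The number of affected events is unknown.

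A reader might infer that the error always makes ASN51 look better tolerated. That does not hold, because a re-worsening recorded as a new event would raise the event count.

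The conclusion about the code rests on a literal reading of section 11.2.3. The conclusions about date and duration rest on the further assumption that the site enters a resolved date whenever it selects that code.

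**What to change.** - In protocol section 11.2.3, remove improvement from the definition of Recovered/Resolved.
- Add a Recovering/Resolving category for events that have improved but are still present. Not recovered/Not Resolved can then keep its present definition without a gap or an overlap.
- Carry the new category into the adverse-event outcome field and into SAP template L_AE1_PG, so that only resolved events show a resolved date.
- Reconcile section 11.2.3 with sections 7.6.1, 10.3.10 and 11.3, so that resolved has one meaning throughout. This is a matter of wording and needs no new clinical follow-up rule.

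The cost is one reworded definition, one added category, and the matching change to the outcome field and listing. A few events will be listed as ongoing for longer.

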### 11.3 Adverse Event Reporting and Follow Up

All AEs (i.e., any new or worsening in severity or frequency of a preexisting condition) with onset after the subject signs consent for trial participation must be promptly documented on the AE electronic case report form (eCRF). Details of the AE must include severity, relationship to study drug, duration, and outcome. Serious Adverse Events Reporting

SAEs must be reported to the Sponsor (or designee) within 24 hours of the knowledge of the occurrence.

An SAE report will be completed as thoroughly as possible including all available details about the event and the signature of the Investigator. The SAE form will be updated when additional information is received.

A death occurring during the trial must be reported to Sponsor or its designee within 24 hours of knowledge of the death whether or not it is considered treatment-related.

The Investigator also must notify the IRB/IEC of the occurrence of the SAE, in writing, as soon as is practicable and in accordance with IRB/IEC requirements and local law. A copy of this notification must be provided to Sponsor or its designee.

Subjects will be instructed to contact the Investigator site and report any adverse events that develop after being discharged from the clinical unit. The Investigator will advise the subject on appropriate treatment, if necessary, and will follow the subject up until the adverse event resolves or the subject is lost to follow-up. If, in the investigator's opinion, the adverse event could be related to sterility issues with  $[^{18}\text{F}]\text{-IMA601}$ , the investigator will inform [REDACTED] In the event of a positive sterility result, [REDACTED] Quality Assurance department will be informed and an investigation following the process as outlined in [REDACTED] standard operating procedures will be initiated.

